## **Statistical analysis**

The analysis plan will include:

- Preliminary analysis consisting of a series of descriptive tables summarising; (a) basic characteristics of the data collected; (b) baseline characteristics of schools and children; (c) attrition rates; and (d) intra-cluster correlation coefficient for the outcomes. This will also include a comparison between participants with detectable levels of cotinine at baseline and zero levels of cotinine at baseline.
- A comparison of the means of the main outcomes at both cluster and individual level after adjusting for the cluster design. We will also adjust for the baseline characteristics and other covariates using generalised estimating equations.

We will only be measuring the salivary cotinine levels of a sample of children at follow up (90% of children who test positive for cotinine at baseline and 10% of children who test negative for cotinine at baseline).

Our principal analysis will be an adjusted analysis of salivary cotinine levels (for children who test positive for cotinine at baseline and remain in the trial – 90% of children who test positive for cotinine at baseline will remain in the trial). Consequently we do not need to adjust the main outcome for multiple testing. For all secondary outcomes we will adopt a more conservative p value (i.e., p = 0.01) to reduce the risk of a type 1 error. We will adjust for the minimisation variables and In terms of the secondary analyses we will adjust for minimisation factors and baseline measures if taken (e.g., quality of life). We will estimate a difference in the mean of salivary cotinine of all children irrespective of their smoking status.

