## **Methods**

This component of the study will estimate the cost of providing the intervention in schools. These costs will include the time of staff involved in programme delivery and materials costs. The estimated costs will be combined with outcome rates to compute a cost-effectiveness ratio. This will take the form of a cost per smoke free child (defined as having zero cotinine levels). However, most of the benefit of this intervention is likely to be in the longer term, with substantial health benefits accruing to the children and possibly their parents. Consequently, we will need to undertake economic modelling to capture these longer term impacts. The longer term follow up will provide estimates of the number of pupils who do not take up smoking in the intervention groups over and above the control scenario. These data can be combined with Quality Adjusted Life Year (QALY) estimates indicating the expected quality of life for smokers and non-smokers to project the potential QALY gains in the intervention group for those pupils who do not take up smoking. We will obtain QALY estimates from the existing literature. Thus, we will assess the QALY losses due to smoking and then estimate the gains that would be achieved should we demonstrate a significant reduction in smoking uptake. The data will also allow the modelling of potential health care cost savings amongst this population, as smokers are known to impose considerable costs on the NHS due to the treatment of smoking-related disease. These costs were estimated at £5.2 billion for the UK in 2005-6, some 5.5% of the total health care budget(43). We will produce Cost Effectiveness Acceptability Curves (CEACs), where we will plot the probability of the intervention against the willingness to pay for a QALY. The current decision rule is that if the cost per QALY has a 50% or greater probability of being less than £20,000 per QALY this is deemed to be cost effective. All future costs and outcomes will be discounted at a rate of 3.5%; however, this will be varied in a sensitivity analysis. We will undertake extensive sensitivity analyses one of which will be a threshold analysis. This will help in estimating the minimum long term effectiveness required by the programme to justify costs.

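### One sentence reads as making the QALY gain conditional on a significant uptake effect, which does not fit the rest of the economic plan or its 50% decision rule

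*Protocol*

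**What the plan says.** All but one of the relevant statements are in the protocol's Economic Evaluation, Methods.

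- **Source of the effect:** "The longer term follow up will provide estimates of the number of pupils who do not take up smoking in the intervention groups", relative to control.
- **Use of the effect:** "These data can be combined with Quality Adjusted Life Year (QALY) estimates indicating the expected quality of life for smokers and non-smokers", as the basis for projecting a QALY gain.
- **The sentence at issue:** as a summing-up, the team will value the QALYs that smoking costs and will "estimate the gains that would be achieved should we demonstrate a significant reduction in smoking uptake".
- **Curves and decision rule:** "We will produce Cost Effectiveness Acceptability Curves (CEACs"), and "if the cost per QALY has a 50% or greater probability of being less than £20,000 per QALY this is deemed to be cost effective".
- **Threshold analysis:** "This will help in estimating the minimum long term effectiveness required by the programme to justify costs".
- **Bootstrap and projection:** individual cost and outcome data are bootstrapped to build the curves, and the trial data are projected forward to expected QALY gains.

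The Statistical analysis section sets the level for significance: "For all secondary outcomes we will adopt a more conservative p value (i.e., p = 0.01"). Smoking uptake is assessed under secondary outcome SO2. Whether tests are one- or two-sided is not stated.

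**The concern.** The sentence at issue sums up how the QALY gain is obtained, and it contains a condition. In this protocol the word significant has a threshold attached, because uptake is a secondary outcome. An acceptability curve is meant to carry the full uncertainty in costs and effects into the decision. A rule that first asks whether the effect is significant answers a different question and discards part of that uncertainty.

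If the condition were followed, the result would be distorted in one of two ways. Without significance, the model has no QALY gain, or a gain set to zero, and a real benefit goes uncredited. With significance, the estimate entering the model has been selected for being large, so the cost per QALY looks too favourable. The protocol does not say what is done when the result is not significant, so the choice between the two procedures could be made after the uptake result is known.

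**Working it through.** **1. Is there a stated figure to reproduce?** No. The protocol gives no power, error rate or sample size for the economic evaluation, and no control-arm uptake or sample size for smoking initiation. What follows is a comparison of statements, then an illustration.

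**2. The statements side by side.**

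| Element of the economic plan | Significance condition? |
|---|---|
| Uptake estimates from long-term follow-up | No |
| Combination with QALY values | No |
| Estimation of the QALY gain (the sentence at issue) | Yes |
| Acceptability curves and 50% rule | No |
| Threshold analysis | No |
| Bootstrap and forward projection | No |

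**3. The two criteria.** A result at two-sided p = 0.01 in favour of the intervention corresponds to 1 - 0.01/2 = 0.995, about 99.5% one-sided certainty that the uptake effect is above zero. The decision rule asks for at least 50% probability that the cost per QALY is below £20,000. These are probabilities of different events, so they cannot be compared as if on one scale. The point is that the first cannot serve as an entry condition to the second without changing the decision.

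**4. Size of the distortion if the condition were applied.**

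Inputs from the protocol:
- 1440 of 2000 children traced into secondary school, or 1000 (50%) under 10% attrition a year (Sample Size Secondary outcomes)
- 50 schools
- odds ratio 1.56 for initiation among children of smoking parents, from a longitudinal comparison of households with and without restrictions
- level 0.01 for secondary outcomes

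Assumptions:
- two-sided testing
- control uptake 10-30%
- ICC for uptake 0-0.05; the protocol gives 0.05 only for cotinine

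Formulas:
- design effect DE = 1 + (N/50 - 1) × ICC; effective number per arm n = (N/2)/DE
- intervention uptake p1 = o/(1 + o), with o = [p0/(1 - p0)]/OR
- SE of the log odds ratio = √[1/(n·p0) + 1/(n(1 - p0)) + 1/(n·p1) + 1/(n(1 - p1))]
- z = ln(OR)/SE; chance of passing = 1 - Φ(2.576 - z)
- overstatement on passing = [z + φ(2.576 - z)/(1 - Φ(2.576 - z))]/z

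Worked case, N = 1440, p0 = 0.20, ICC = 0.05:
- DE = 1 + (28.8 - 1) × 0.05 = 2.39; n = 720/2.39 = 301.3
- o = 0.25/1.56 = 0.160; p1 = 0.138
- SE = 0.2205; z = 0.4447/0.2205 = 2.02
- chance of passing = 0.29; overstatement = 1.59-fold

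Ranges for OR 1.56, control uptake from 10% to 30%:

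| N | ICC | Chance of passing | Overstatement of log OR |
|---|---|---|---|
| 1440 | 0 | 39% to 86% | 1.43- to 1.07-fold |
| 1440 | 0.05 | 14% to 42% | 2.08- to 1.40-fold |
| 1000 | 0 | 25% to 68% | 1.67- to 1.17-fold |
| 1000 | 0.05 | 11% to 35% | 2.24- to 1.49-fold |

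If gains were set to zero whenever significance was missed, a true effect of this size would be credited with no QALYs in the complement of the third column, 14% to 89% of trials.

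**The case against.** The strongest reply is that the sentence is only loosely worded. It can be read as describing what a demonstrated reduction would be worth, and one clause is set against several unconditional commitments that already amount to the right analysis. That reading is available, and it limits the point. The protocol nowhere says that modelling is skipped or gains set to zero above a p-value threshold.

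A reader might infer more than the text bears in four ways.

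- **That QALY gains are estimated only if uptake is significant.** The word only is absent, and the surrounding text plans the modelling regardless.
- **That Objective 4 would go unanswered.** Table 1 maps Objective 4 to question 1G, on exposure to second-hand smoke. The cost per smoke-free child, defined by zero cotinine, answers that without uptake or QALYs.
- **That the acceptability curves are invalid.** They would be so only if actually filtered on significance, and the bootstrap description contains no filter.
- **That the illustrated overstatement is a property of the plan.** It depends on the condition being applied and on assumed inputs. At ICC 0 and 30% uptake it nearly vanishes. The odds ratio is also not a randomised-arm effect; since the intervention will not change every home, the arm-level effect may well be smaller.

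It is also true that the economic section names no significance level; 0.01 is carried over from the Statistical analysis section.

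What the reply does not remove is the inconsistency. A condition is written down, it governs the step that produces the QALY gain, and nothing says which procedure prevails.

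**Conclusion.** The point holds as an internal inconsistency, with a bias that arises only if the condition is applied. The sentence conflicts with the unconditional curves, bootstrap, projection and threshold analysis in the same section, and it does not fit the 50% rule. Under a strict condition at two-sided p < 0.01, with OR 1.56, control uptake 10-30%, 1000-1440 children and ICC 0-0.05, the effect would reach the model in 11-86% of trials and be overstated about 1.07- to 2.2-fold on the log odds scale when it did. Control uptake, the ICC for uptake and two-sidedness are assumptions, so these figures show the possible size and do not predict this trial's result. The consequence is confined to the long-term QALY part of the economic evaluation.

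**What to change.** In Economic Evaluation, Methods, delete the closing conditional clause of the sentence on QALY losses and gains. In its place, state that the estimated uptake difference between arms and its uncertainty enter the model whatever the p-value, and that the acceptability curve and threshold analysis are reported in all cases. This costs a wording change only: no new data, and no modelling beyond what is already planned. It should be made before the long-term uptake results are seen.

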## **Ethical arrangements**

#### Rationale for carrying out this research

The Smoke Free Homes intervention has the potential to address a major public health issue i.e. second-hand smoke and its influence on the health of children. Given that this is now a problem largely among families with socio-economic disadvantage in the UK, the intervention also has a potential to address the health gap between rich and poor. However, there is no evidence for its effectiveness and cost-effectiveness that is based on objective outcome measure (cotinine test). Therefore these research questions address a priority need for deprived communities where both active and passive smoking are common.

Cost justification: If SFH is found effective in our study, it would provide justification to continue to expand this scheme which could potentially cost only 3 million pounds per year approximately at a national level. However, if found ineffective, the NHS would be able to divert this money to other cost-effective strategies. The low cost of intervention should not be a deterrent to invest in a robust evaluation. A cheap intervention, if found effective, is likely to be highly cost-effective. Developing robust evidence for the cost-effectiveness of a cheap intervention provides good value for money.

#### Children's participation

We understand that children's participation in such studies raises issues around incompetence, vulnerability and powerlessness. We will ensure that our approach to children is participatory and as less intrusive and confrontational as possible. In addition, our research team has previous experience of working with children.

#### Any changes in the routine that may be potentially harmful

No participating child or family will be deprived of any service that she or he would ordinarily receive. There will be no extra burden, financial or otherwise, on the participants. Children or their families will not incur any cost for participating in this study. They will not receive any financial incentive to participate in the CLASS trial, although they will receive a small sum of money for taking part in the additional qualitative elements of the study (£20 per participant taking part in teacher or parent focus groups, £20 for the parents of children taking part in a focus group, £50 per family taking part in family interview). Travel expenses will be reimbursed

#### Potential harms related to intervention

This is not a clinical trial. The educational messages in SFH programme are not harmful. We have explored initial concerns about the potential of children confronting their families about their smoking behaviour. In our feasibility study, no adversities were highlighted by the children or parents in focus group discussions. However we have made provisions for families to be referred to a family counsellor, if they feel the intervention has caused any issues which need to be discussed further.

#### Primary outcome and Sample size

We have selected salivary cotinine test as the primary outcome. Cotinine is the only objective measure that can detect the difference between active and passive smoking and therefore, be used as a valid measure in this study. Any alternative measure selected as primary outcome for this study will compromise its validity and invariably make the study less ethical. Providing the saliva sample for salivary cotinine testing is also not harmful to children.

Under-powered trials are considered unethical; therefore our sample size calculations are based on conservative estimates and high power. We have also taken account for the potential attrition.

#### Confidentiality and anonymity of participants

All efforts will be made to maintain participant confidentiality. All data collected will be anonymised, being identified with a unique participant identification number only. Data entered in databases will be password protected and will not contain any other identifiable information other than the unique identification number. A copy of the database will be kept on the York Trials Unit's secure server. Copies of paper data will be preserved until the youngest child in the study is at least 21 years. We will ensure that participants' names and identifiable information remain confidential and remains locked in a cupboard in YTU separate from all other study data at all times. The only occasions that this information will be used are to identify children for first and subsequent follow-ups or in case of any adverse incident. While retrieving information to identify children for follow up, we will ensure that our lists only contain their unique identifier number and not any other information such as cotinine test results. This will preserve anonymity of participants' results even from the investigators. We will also ensure that no such information is presented in any reports or other materials. In the unlikely event that something was disclosed, either during the qualitative work or on completed surveys, which required action, such as reporting to Social Services, then confidentiality would have to be broken. The appropriate action would be taken, including reporting the issue as an Adverse Event (AE) or Serious Adverse Event (SAE). This has been made clear on the participant information sheets.

#### Informed consent and no obligation to participate

Schools will receive written information and will also have an opportunity to meet the trial coordinators. A written consent form will be obtained in they agree to participate. Schools will be made aware that they can leave the study at any time without giving a reason.

Informed consent on an opt-out/withdraw basis will be sought from parents to obtain saliva from their children to measure cotinine; and to conduct children surveys about children's exposure to second hand cigarette smoking. Parents will have the right to withdraw their child from the research at any stage with no consequences. Parents will be sent written information on all aspects of the research project. It will be made clear that parents and their children are under no obligation to participate in the study and no change in their routine education will take place if they refuse to participate. Parents will be told that any information disclosed will be treated with confidentiality. Parents will also hopefully be able to watch a short DVD clip on the trial website explaining the study. We will ask parents to discuss the trial with their child/children. If either parents or children are unwilling or unable to take part in the study, we will request parents send us a withdrawal form in a self-addressed envelope or call/text/email us using the contact details provided within the information pack. Just before data collection, we will send another reminder one-page letter though schools, to parents (for whom no opt-out consent forms have been received), indicating the date for the data collection and SFH activities, and requesting them to either call/text/email us or send us a withdrawal form if they would like to withdraw their child/children from the study at any stage.

Children will also be provided with age appropriate written information at school, which we will ask the school teacher to take them through. We will also provide a short DVD clip which can be shown to the children in class.

After speaking to several staff members at the potential participating schools, we have learned that getting parents to engage with school activities and return forms is a recurring difficulty, not just with research consent forms, particularly in schools in deprived areas. We believe that this opt-out approach is ethical, as it will allow us to recruit the required number of participating children (therefore meet the sample size requirements) and use the most valid measure to complete this study of high public health importance. We have built enough safeguards in our research procedures to maintain complete confidentiality and anonymity to the highest possible degree, inform parents

sufficiently and regularly and provide them plenty of opportunities to withdraw their child at all stages of the study.

#### Additional information

All participating children will be involved in the SFH classroom activities about passive smoking. These activities are consistent with activities within the Key stage 2 of the National Curriculum. As part of developing a healthy, safer lifestyle within Key stage 2, pupils should be taught: (a) what constitutes a healthy lifestyle, including the benefits of exercise and healthy eating, what affects mental health, and how to make informed choices; (b) which commonly available substances and drugs are legal and illegal, their effects and risks; (c) to recognise the different risks in different situations and then decide how to behave responsibly, including sensible road use, and judging what kind of physical contact is acceptable or unacceptable; (d) that pressure to behave in an unacceptable or risky way can come from a variety of sources, including people they know, and how to ask for help and use basic techniques for resisting pressure to do wrong; school rules about health and safety, basic emergency aid procedures and where to get help.

Schools in Yorkshire have previously taken part in Smoke Free Homes. If schools have agreed to take part in the research we envisage that all children within the school will take part in the Smoke Free Homes activities. This is consistent with usual school procedures and the method adopted in pilot work. However, given that the classroom activities still form part of a research project, parents will be given the right to choose to withdraw their child from this element of the research. Thus an 'Opt Out' approach will be used for the intervention too. This is consistent with procedures for parental rights to withdraw children under the age of 15 years from sex education lessons.

The SFH intervention is designed to raise children's awareness about the harmful effects of passive smoking and empower them to influence their home and car environment. There is a potential risk that we may raise their anxieties and potentially cause distress amongst families. In our exploratory study of SFH, we carried out focus groups with parents as well as children. We specifically asked parents: "Did you feel comfortable/ happy to discuss the issue with your children if it was raised by them? If no, why not? Does it create tension or interfere with parenting roles?" We asked children: "Did you feel comfortable/ happy to discuss the issue with your parents/other household members? If no, why not?". The analysis of these focus groups has given us some insights into the receptivity of the issue amongst families who chose to participate. Children felt confident in raising the issue of second-hand smoking with parents. Parents also did not find this an "awkward" discussion. However, we will be vigilant in our preparation of parents and children who might wish to participate in the trial and will ask similar questions in the focus groups to spot any potential tensions. We have also built-in support from Leeds Family Therapy Training Unit for this project. All family interview participants will be provided with contact details for a family counsellor.

Children will be asked to return signed promise forms back to the teachers. However, all children will be given a 'gold certificate' for taking part in the smoke free homes programme. Children who are not able to return signed promise forms will also be appreciated and 'rewarded' as above.

We have consulted with the chair of the ethics committee ([name]) at the Faculty of Medicine and Health, University of Leeds. He has kindly agreed to be an independent ethics advisor to our research team.

It is important that we are able to respond appropriately should any participant express a wish to quit smoking, either through the qualitative work or on completed surveys. In the case of children, we are unable to send a letter to them as this would break confidentiality; we have therefore suggested that children should contact their school nurse or a member of staff at school should they

wish to discuss any issues related to smoking. This guidance will be given on each survey they are asked to complete. We envisage the role school nurses will play in the trial as very minimal. We expect most children to speak to a teacher they know at school. The school nurse would only be expected to carry out normal responsibilities and procedures should a child approach them.

